16.7 Data confidentiality

The research team will ensure that participants' anonymity is maintained on all documents. Data will be collected and stored in accordance with the current legal and regulatory documentation.

Electronic study records will be stored in a SQL server database, stored on a restricted access, secure server maintained by Plymouth University. Data will be entered into the database via a bespoke web-based data entry system encrypted using SSL. Access to electronic data will be permission based, with access to identifiable information limited to those processing questionnaires and performing initial screening activities. Data entered onto the database will be backed up according to PenCTU SOPs.

Within the CTU, anonymised paper-based study data will be stored in locked filing cabinets within a locked office. Any paper-based participant related identifiable data will be stored separately from the

study data. Copies of study data retained at study sites will be securely stored for the duration of the study prior to archiving.

Identifiable information will be omitted from the transcriptions of the process evaluation interviews.

16.8 Access to data

The CTU data team will have access to the full dataset, including identifiable data. Site based researchers will have access to the dataset for participants from their site, including identifiable information, to perform screening activities. Other members of the study team and the CTU will have restricted access to anonymised study data. Access will be granted to the Sponsor and host institution on request, to permit study-related monitoring, audits and inspections. Access to the database will be overseen by the CTU data manager and trial manager.

16.9 Archiving

Following completion of data analysis and submission of the end of study report, the Sponsor will be responsible for archiving the study data and essential documentation in a secure location for a period of five years after the end of the trial. No trial-related records should be destroyed unless or until the Sponsor gives authorisation to do so.

17 STATISTICAL CONSIDERATIONS

17.1 Sample Size

Since the primary analysis is a comparison in each allocated group of the proportions of the primary binary outcome, the sample size is calculated for a two-sided Fisher exact test. An abstinence rate of 5% for the control group, and detectable effect of 6% (i.e.: an increase from 5% to 11% due to the intervention) are conservative estimates consistent with those from the EARS pilot study and those reported from a systematic review of pharmacological interventions. The corresponding odds ratio for this effect is 2.35. Participants with missing outcome data will be assumed to be still smoking, and the number of participants in each allocated group are assumed to be in the ratio of 1:1. Under these conditions, according to Stata v14.2, the minimum number of participants required to detect an abstinence rate of 11% compared to that of 5% in the control group with a significance level of no more than 5% and power of at least 90% is exactly 900, above which a power in excess of 90% is maintained (Figure 1). The Stata code and the R code used to verify this calculation is found in Appendix 2.

TARS Protocol Version 2 26OCT2017

[figure not shown]

Figure 1: Plot of power of test afforded by each sample size ranging from 884 to 916, for equal group sizes and 5% significance level, where the proportion of CO-confirmed abstinence rates at 9 months is 0.05 and 0.11 in the control and intervention group, respectively.

17.2 Statistical analysis

The reporting and presentation of this trial will be in accordance with the appropriate CONSORT guidelines [79, 80] and in line with the Russell Standard schedule [6], with the primary comparative analysis being conducted on an intention-to-treat basis. All comparative analyses will allow for potential clustering by site and/or GP surgery and/or trainer, adjusting for important baseline covariates of socioeconomic status and recent quit attempts as well as the other stratification factor 2-item Heaviness of Smoking Index (HSI) [74]. Further exploratory analysis will also account for partial clustering in the intervention group by research staff within each site.

For completeness, unadjusted between-group comparisons will also be presented, based on chisquared tests to compare binary outcomes (e.g. abstinence rates) and two sample t-tests to compare continuous outcomes (e.g. daily cigarette consumption) [74]. The between-group comparisons of smoking abstinence rates (and other secondary binary outcomes) will be expressed as odds ratios with 95% confidence intervals; the relative risk and corresponding confidence interval will also be presented as a more intuitive measure of the size of the intervention effect.

Where hypothesis tests are carried out, these will be at the 5% level for primary and secondary outcomes, and the 1% level for interaction terms. No adjustment for multiple analyses will be made; such adjustment methods are too conservative when outcomes are positively correlated, as they would be in this trial.

17.2.1 Baseline characteristics

Baseline characteristics of participants will be summarised, with descriptive statistics used to assess any marked baseline differences in demographics or outcome measures between the two allocated groups. Loss to follow-up after randomisation will be reported separate for each allocated group, and baseline characteristics examined to assess for potential bias.

17.2.2 Primary analysis of primary outcome

The primary analysis will be a logistic comparison of the primary outcome of CO-confirmed abstinence at 3 and 9 months post-baseline, using a mixed-effects model to account for clustering by site, with the adjustment for the HSI stratification factor, as well as important baseline covariates (i.e. age, gender, socio-economic status, level of smoking, recent quit attempts. Interpretation of the

TARS Protocol Version 2 26OCT2017

primary effectiveness will be based on the adjusted odds ratio from this model, and the point estimates reported with 95% confidence intervals. Those participants with missing outcome data will be assumed to be still smoking [6].

17.2.3 Secondary analysis of primary outcome

Although the trial is not powered to detect the influence of moderating factors on the primary or secondary outcomes, secondary analyses will be undertaken to explore whether the intervention effect is modified by sociodemographic and/or behavioural factors (e.g. age, gender, socio-economic status, baseline HSI, MVPA level, and confidence to quit). These analyses will be undertaken for the primary outcome and for the reduction in smoking (both the actual reduction and the proportion of participants reporting \geq 50% reduction in smoking level). The multi-variable models outlined above will be extended to include the interaction term of allocated group and the potential modifying variable, tested at the 1% significance level. However, such analyses will have low statistical power and likely to yield false positive findings, so the results will need to be conservatively interpreted. We will also conduct a sensitivity analysis to determine if the intervention dose actually received influenced differences in outcomes.

17.2.4 Analysis of secondary outcomes

Between-group comparisons will be undertaken at 3 and 9 months post baseline for all available outcome measures, and only prolonged abstinence rates at 15 months. Analysis will use multivariable logistic regression to compare these secondary outcomes between allocated groups, with adjustment for the stratification factors [site, HSI], as well as important baseline covariates (i.e. age, gender, socio-economic status, level of smoking, recent quit attempts).

The between-group comparisons of continuous outcomes (e.g. daily cigarettes smoked, minutes of MVPA) will be reported as mean differences together with 95% confidence intervals, unless the outcomes are substantially skewed. Multi-variable linear regression will be used to compare continuous variables between allocated groups, with adjustment for the stratification factors, important baseline covariates, and baseline outcome values, where relevant.

Sensitivity analysis will examine the potential influence of participants lost to follow-up under varying assumptions. Further sensitivity analysis may be undertaken if any marked imbalance between allocated groups is seen in important baseline characteristics, by further adjustment for such baseline characteristics in the multi-variable models detailed above.

Finally, we will conduct exploratory mediational analysis to determine if any effect of trial arm on the primary outcome was mediated by changes in smoking, physical activity, from baseline to 3 months. We will also examine if changes in smoking and physical activity are mediated by changes in various secondary outcomes (eg, importance and confidence to reduce smoking/increase physical activity; self-monitoring and goal setting; cravings)

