A recent pilot trial [1], conducted by the applicants, randomised 99 smokers, who wished to reduce smoking but not quit, to receive advice on smoking reduction/cessation (control) or client-centred behavioural support (by phone or face-to-face) for smoking reduction and increasing physical activity (intervention). Exploratory analysis [52] revealed the intervention group, compared with control, were significantly more likely to achieve at least 50% reduction in number of cigarettes smoked (39% vs 20%), to attempt to guit (22% v 6%), be abstinent up to 8 weeks after guit day (14% vs 4%), and be abstinent at 16 weeks (10% vs 4%). A higher proportion of the intervention group also reported using physical activity for controlling smoking: 55% vs 22% and 37% vs 16%, at 8 and 16 weeks, respectively. Delivery of the intervention was regarded by both providers and recipients as feasible and acceptable, with the focus on reduction rather than cessation being a particularly valued aspect, and important for trial recruitment [2]. The participants used a variety of behavioural smoking reduction strategies, sometimes supported with changes in physical activity, to control cravings [51]. Exploratory cost-effectiveness analyses, using data from the pilot trial, indicated that, if the results were replicated, the intervention would be considered cost-effective in an NHS setting. The study also provided valuable information about trial recruitment [52], retention [53] and intervention engagement [1] and fidelity [54]. In the pilot study, smokers were excluded if they wished to use NRT and survey data [12] suggest up to 25% of smokers would now be ineligible (for the proposed study) if we excluded smokers using either NRT or e-cigarettes in the proposed study. This would be a sizeable proportion and their exclusion may limit the generalisability of the findings, as well as adding constraints on recruitment. Further reviewing of the literature suggests that exercise still acutely reduces cravings while using NRT [55], and smokers often use a combination of pharmacological and behavioural approaches for reduction. We therefore propose to include those using NRT and ecigarettes in this definitive study. By assessing self-reported use nicotine products and engagement in physical activity we will conduct sensitivity analyses to examine the impact of NRT/e-cigarette use on the findings.

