8.7 Baseline

Following receipt of informed consent study participants will be invited to complete baseline assessments. The baseline assessments will either be completed at a face-to-face screening/consent visit (as described above), or be mailed to participants in the form of a questionnaire booklet, with a cover letter, and freepost return envelope. If the booklet is mailed to the participant the opportunity will be given for participants to complete the questionnaire booklet over the telephone with a member of the local research team, if they would prefer. Randomisation will depend upon CTU receiving a completed baseline questionnaire booklet from the potential participant. A shopping voucher will be mailed to all participants upon CTU receipt of the completed baseline questionnaire booklet.

The baseline questionnaire booklet contains questions relating to the following:

- Smoking behaviour
- Importance and confidence in smoking reduction and cessation
- Importance and confidence in being physically active
- Availability of support to reduce smoking and increase physical activity
- Use of physical activity for smoking regulation
- Self-reported physical activity (7-day physical activity recall)
- Planning to change smoking
- Planning to change physical activity
- Self-monitoring of smoking
- Self-monitoring of physical activity
- Urges & strength of urge to smoke
- Use of e-cigarettes and NRT (nicotine replacement therapy) products
- Health related quality of life (EQ-5D-5L & SF12)
- Self-reported height and weight (BMI)
- · Health service utilisation and costs, including smoking related costs

Self-reported health & social care utilisation costs

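### Section 17.2.4 adjusts continuous outcomes for their baseline value but leaves it out of the logistic models, which gives up some power for binary outcomes also asked at baseline

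*Protocol*

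**What the plan says.** Protocol section 17.2.4 sets one rule for each type of model.

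- **Binary outcomes:** "Analysis will use multivariable logistic regression to compare these secondary outcomes between allocated groups, with adjustment for the stratification factors [site, HSI", plus a list introduced by *i.e.*: age, gender, socio-economic status, level of smoking and recent quit attempts. The outcome's own baseline value is not listed.
- **Continuous outcomes:** linear regression "with adjustment for the stratification factors, important baseline covariates, and baseline outcome values, where relevant".

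The baseline booklet (section 8.7) asks about "Use of e-cigarettes and NRT (nicotine replacement therapy) products" and "Use of physical activity for smoking regulation". By the schedule in section 10.6, the first is asked again at 3, 9 and 15 months and the second at 3 months. Use of e-cigarettes and NRT is a listed secondary outcome (sections 4 and 7.5). Use of physical activity for smoking regulation is a process measure (section 7.5).

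Section 17.2.4 also allows a sensitivity analysis with further adjustment. It is optional and depends on a marked baseline imbalance being seen.

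**The concern.** Adjusting for an outcome's baseline value is the usual way to use what is already known about a participant. The protocol accepts this for continuous outcomes and, without giving a reason, leaves it out of the logistic models one paragraph earlier. Because that covariate list is closed, a SAP that followed it literally would omit the baseline value.

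Users of nicotine products enter the trial by design: section 8.4 admits smokers whatever other nicotine products they use. Section 5.1.6 gives an idea of how many: "survey data [12] suggest up to 25% of smokers would now be ineligible" had users of NRT or e-cigarettes been excluded. Someone using such a product at entry is plausibly more likely to report using it later, and no listed covariate records prior use directly. If so, the planned model gives up power. It also lets a chance difference in baseline users feed into the estimated effect.

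**Working it through.** **The plan's own figure.** The protocol gives no power or precision figure for these outcomes. Its only sample-size figure is for the primary outcome, where "the sample size is calculated for a two-sided Fisher exact test" at 5% versus 11%. Exact enumeration gives power 0.9003 at N = 900 and 0.8995 at N = 898, so 900 is reproduced. Nothing below changes it.

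**Inputs from the protocol**
- Baseline use of NRT or e-cigarettes: q = 0.25. Section 5.1.6 states this as an upper figure.
- Follow-up at 3 months: 60-65% (section 10.4), so 0.60 × 450 = 270 to 0.65 × 450 ≈ 292 per arm.

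**Assumptions (not in the protocol)**
- The item is scored yes/no.
- Use at follow-up is 25% in control and 35% with the intervention.
- The correlation φ between baseline and later use in the control arm is 0.2 to 0.6.
- No other covariates are in either model.

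**Step 1: model without the baseline value.** OR = (0.35/0.65)/(0.25/0.75) = 1.615, so log OR = 0.480.

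SE = √[1/(270 × 0.25 × 0.75) + 1/(270 × 0.35 × 0.65)] = √(0.01975 + 0.01628) = 0.190.

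Power = Φ(0.480/0.190 − 1.96) = Φ(0.57) = 71.4%.

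**Step 2: model with the baseline value.** Baseline and follow-up use in control are both 25%, so control use is 0.25 + 0.75φ in baseline users and 0.25 − 0.25φ in non-users. A common conditional OR is chosen so that overall use in the intervention arm is 35%. In each baseline stratum v₀ and v₁ are n·p(1−p) in the two arms. The information is the sum over strata of v₀v₁/(v₀ + v₁), and SE is its inverse square root.

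Example, φ = 0.6: control use is 0.70 and 0.10, and the conditional OR is 2.11, giving 0.831 and 0.190 with the intervention.
- Baseline users (67.5 per arm): v₀ = 14.2, v₁ = 9.5, information 5.7.
- Non-users (202.5 per arm): v₀ = 18.2, v₁ = 31.2, information 11.5.
- SE = 1/√17.2 = 0.241, and power = Φ(ln 2.11/0.241 − 1.96) = Φ(1.13) = 87.0%.

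| φ | Conditional OR | SE of log OR | Power with baseline | Gain over 71.4% (points) | Equivalent sample saving |
|---|---|---|---|---|---|
| 0 | 1.62 | 0.190 | 71.4% | 0 | 0% |
| 0.2 | 1.65 | 0.194 | 73.2% | 1.8 | 4% |
| 0.3 | 1.70 | 0.200 | 75.4% | 4.0 | 9% |
| 0.4 | 1.77 | 0.209 | 78.5% | 7.1 | 16% |
| 0.5 | 1.90 | 0.222 | 82.4% | 11.0 | 24% |
| 0.6 | 2.11 | 0.241 | 87.0% | 15.6 | 33% |

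With 292 per arm, power is 74.8% without the baseline value and 76.5% to 89.5% with it (φ 0.2 to 0.6).

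**Step 3: where the gain lies.** The SE of the log OR rises with adjustment, from 0.190 to between 0.194 and 0.241. Power improves because the conditional log OR grows faster than its SE. The interval for the OR does not narrow.

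**Step 4: use of physical activity for smoking regulation, if scored yes/no.** The pilot's 16-week rates were 37% versus 16% (section 5.1.6). At 16% versus 37% with 270 per arm, power is about 100% with or without the baseline value. At an assumed 16% versus 26%, with 16% also assumed at baseline, power is 80.8% without it and 82.4% to 92.7% with it (φ 0.2 to 0.6).

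**Step 5: chance imbalance.** The SD of the between-arm difference in baseline users is √(2 × 0.25 × 0.75/270) = 3.7 points. With equal baseline and follow-up prevalence, about φ times this passes into the unadjusted difference: 0.2 × 3.7 = 0.7 to 0.6 × 3.7 = 2.2 points (one SD).

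**The case against.** - **Binary scoring is inferred.** The protocol does not say how either item is scored. If they are analysed as amounts or scales, the linear rule applies and the baseline value is already in. Scoring and outcome-specific covariates are normally SAP matters, and the SAP is not shown. This stands, so the point is limited to outcomes that are analysed as binary. It does not remove the point, because the protocol itself states a closed list for one model type.
- **The binary outcomes the protocol names do not need the clause.** Everyone smokes at least 10 cigarettes a day at entry (section 8.4), so abstinence and 50% reduction have no varying binary baseline value, and smoking level is already in the model. This stands.
- **The outcomes affected are minor.** Section 6 speaks of quantifying nicotine-product use and does not list use of activity to control smoking among its aims. That item is a process measure. This stands and lowers the severity.
- **The size is assumed.** Persistence of use is not given, and 25% is an upper figure. Listed covariates such as recent quit attempts may carry part of the same information, so the loss against the planned model may be smaller. This stands.

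Two stronger readings are tempting. A reader might infer that precision of the odds ratio is thrown away; step 3 shows that its SE rises with adjustment. A reader might also infer that the planned comparison is biased. Randomisation keeps it valid with or without the baseline value, and chance imbalance is part of the sampling error that the test already allows for.

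**Conclusion.** The point holds as a low-severity inconsistency. Section 17.2.4 adjusts linear models for the baseline outcome and fixes logistic covariates that leave it out. The roughly 2 to 16 points of lost power rest on yes/no scoring, 25% versus 35% use, 270 per arm, a correlation of 0.2 to 0.6 and no other covariates. The loss shrinks to nothing as the correlation falls to zero, and for physical-activity use it is negligible at an effect of the pilot's size. The existing fallback is discretionary and triggered by the data, so it does not recover power in the main comparison. The primary outcome, the abstinence outcomes, 50% reduction and the sample size of 900 are unaffected.

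**What to change.** In section 17.2.4, extend the logistic regression sentence to match the linear one by adding, after the covariate list: *and baseline outcome values, where relevant*. In practice this covers e-cigarette use, NRT use and, if scored yes/no, use of physical activity for smoking regulation. The cost is one clause: the items are already in the baseline booklet, and no extra data or participants are needed. Settle it before allocation is revealed for analysis, so that the covariates are not chosen after the results are seen. The adjusted odds ratio will then be conditional on baseline use and should be reported as such, beside the unadjusted comparison that section 17.2 already promises.

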7.5 Secondary outcomes

Point prevalence CO verified abstinence at 3, 9 and 15 months post baseline

Only those reporting abstinence by mailed survey at 3 and 9 months will be contacted for CO verification. Only those abstinent at 9 months will be followed up at 15 months by mailed questionnaires and if abstinent by face-to-face assessment of expired CO.

Self-reported smoking and use of aids to reduce/quit smoking

Study participants will be asked to self-report the number of cigarettes smoked and type of nicotine product, i.e. pipes, cigars and roll your own. The same formula used in the EARS pilot study will be used to convert amount of loose tobacco into number of cigarettes [1].

Questions to capture use of e-cigarettes and NRT (nicotine replacement therapy) products

Physical activity

Questions at baseline, 3 and 9 months will assess self-reported 7-day physical activity recall. A sub set of all participants in the TARS study will be invited to wear an accelerometer for a 7 day period during the study. The accelerometer, and instructions for use will be mailed to selected participants at the 3 month time point from CTU, along with the 3 month questionnaire booklet. The accelerometer is waterproof, and is worn continuously for 7 days. At the end of the 7 days the participant should return the accelerometer to the CTU in the freepost envelope provided.

Self-reported height and weight - Body Mass Index (BMI)

At baseline, 3 and 9 months participants will be asked to self-report their height and weight. The questions will be part of the questionnaire booklet mailed to participants from CTU at baseline, 3 and 9 months. Based on the weight and height reported we will derive a measure of BMI.

Health related quality of life (EQ-5D-5L & SF-12)

EQ-5D-5L

This is described in section 19.1.

SF-12

The SF-12 is a 12-item, patient-reported survey of patient health, consisting of twelve questions [70]. In this study participants will be asked to complete the SF12 as part of the questionnaire booklet mailed to them from CTU at baseline, and then at 3 months follow-up and 9 months follow-up.

Health economic outcomes

Health service utilisation and costs, including smoking related costs

Process measures

The following process measures will also be assessed as part of the self-report questionnaire booklets issued to all participants by CTU at the baseline and 3 months:

- Importance and confidence in smoking reduction and cessation

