10.4 Loss to follow-up

Based on the data from the TARS pilot study (EARS) [1] it is anticipated that 60-65% of TARS participants will complete follow-up at 3 months.

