17.2.5 Termination of the trial

Based on recruitment rates from the EARS pilot study, it is estimated that 20 smokers a month can be recruited for 12 months from each of the four recruitment sites. However an interim analysis of the recruitment rate is planned at the end of the internal pilot-trial phase at four months after the start of the study. Progression will be decided according to the scenarios set out in Table 2, Section 11. Achievement of a single criterion, but not the other, requires discussion about progression. A figure of <50% for recruitment could only lead to progression if the internal pilot phase duration was

extended due to especially encouraging recruitment or engagement in the latter part of the planned 4 month internal pilot window. Results from the process evaluation will help inform decisions regarding progression, where further discussion is required, as well as any changes needed to address a shortfall in the number of recruited participants.

In addition to a review of recruitment and engagement at 12 months, the follow-up rate at the 3 month assessment will also be assessed. We propose no progression if we don't achieve at least a 50% response rate at 3 months, discussion about progression if between 50-64% and automatic progression (with agreed plans to improve it) if we achieve at least a 65% response rate.

A futility analysis is planned nine months after the 12-month recruitment phase ends. This analysis will assess for a difference in the primary outcome between allocated groups, that is: the proportions of participants achieving CO verified prolonged abstinence at 3 and 9 months post baseline. If there is evidence of a statistically significant difference (p<0.05) between allocated groups, then the trial will continue and all participants abstinent at nine months will be followed-up again at 15 months post baseline, and the total trial duration will be 44 months. If there is insufficient evidence of a significant intervention effect at 9 months, then the 15 month follow-up will be abandoned and the trial duration will be 39 months, with a corresponding saving in resources.

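### Continuous outcomes measured at both 3 and 9 months would be better analysed in one repeated-measures model than in separate regressions that drop anyone without a value at that visit

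*Protocol*

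**What the plan says.** Section 17.2.4 sets the timing: "Between-group comparisons will be undertaken at 3 and 9 months post baseline for all available outcome measures". It also sets the method: "Multi-variable linear regression will be used to compare continuous variables". The model is to adjust for site and HSI, the main covariates and, where it applies, the outcome's own baseline value. Effects are reported as mean differences with 95% confidence intervals unless an outcome is substantially skewed. No term links a participant's two follow-up values, and no imputation is named for continuous outcomes.

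On missing data, the same section adds: "Sensitivity analysis will examine the potential influence of participants lost to follow-up under varying assumptions". Section 17.2.1 promises loss to follow-up by arm and a look at baseline characteristics for bias. The rule in 17.2.2, "Those participants with missing outcome data will be assumed to be still smoking", belongs to the primary outcome and supplies no value for activity, quality of life or weight. The clustering clause in 17.2 concerns site, GP surgery and trainer, not repeated values within a person.

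On expected response, section 10.4 says "it is anticipated that 60-65% of TARS participants will complete follow-up at 3 months", and section 17.2.5 says "We propose no progression if we don't achieve at least a 50% response rate at 3 months". No 9-month rate is given.

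**The concern.** The booklets at baseline, 3 and 9 months (8.7, 10.1, 10.2, 10.6) cover smoking behaviour, 7-day activity recall, height and weight, EQ-5D-5L and SF-12. Section 6 names self-reported activity, quality of life and weight at 3 and 9 months among the trial's aims. A linear regression of the 9-month value uses only people who have one, so someone who answered at 3 months and then fell silent contributes nothing to the 9-month estimate.

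Two things are at stake. The smaller is precision, because collected data go unused. The larger is bias: if 9-month return depends on how a person was doing at 3 months, and does so differently in the two arms, the 9-month responders are no longer comparable. That is plausible here, though not shown. Participants are not blinded (8.8), data come by post, and only the intervention arm has Health Trainer support (9.1).

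**Working it through.** **Figures the protocol gives.** There is no SD, correlation or power statement for any continuous outcome, so there is no figure on this point to reproduce. The one sample size given does reproduce: exact enumeration of the two-sided Fisher test for 5% v 11% gives power 0.8995 at 449 per arm and 0.9003 at 450, that is N=900. Expected 3-month responders per arm are 0.60 × 450 = 270 to 0.65 × 450 = 292.5.

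**Assumptions.** 450 per arm; values in SD units, lower being better; true effect -0.3 SD; correlation of each follow-up with baseline 0.5; correlation between 3 and 9 months 0.6 or 0.8; about 62-64% returning at 3 months and 50-58% at 9 months. There were 1,000 simulated trials per row. Separate means baseline-adjusted regression on responders. Joint means maximum likelihood for both visits, with arm-by-time and baseline-by-time terms and unstructured covariance.

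| What 9-month return depends on | Corr. 3-9 | Returned 3 / 9 mo | 9-mo bias, separate / joint | 9-mo SE, separate / joint |
|---|---|---|---|---|
| Chance; 80% of 3-month responders return | 0.6 | 62% / 50% | 0.000 / 0.000 | 0.0827 / 0.0810 (-2.1%) |
| Same | 0.8 | 62% / 50% | 0.000 / -0.001 | 0.0834 / 0.0794 (-4.8%) |
| Chance; independent at the two visits | 0.6 | 62% / 58% | +0.002 / +0.002 | 0.0757 / 0.0735 (-2.9%) |
| Same | 0.8 | 62% / 58% | +0.003 / +0.004 | 0.0736 / 0.0674 (-8.5%) |
| 3-month value, same in both arms | 0.6 | 62% / 51% | +0.013 / +0.002 | 0.0800 / 0.0790 (-1.2%) |
| 3-month value, intervention arm only | 0.6 | 62% / 52% | -0.048 / +0.001 | 0.0778 / 0.0769 (-1.1%) |
| Same | 0.8 | 62% / 52% | -0.078 / -0.001 | 0.0775 / 0.0755 (-2.6%) |
| Unseen value, intervention arm only | 0.6 | 64% / 55% | -0.160 / -0.146 | 0.0762 / 0.0748 (-1.8%) |
| Same | 0.8 | 64% / 55% | -0.204 / -0.168 | 0.0774 / 0.0752 (-2.8%) |

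In the rows where return depends on the 3-month value, its log-odds are 1.7 - 1.0 × that value; where only the intervention arm is affected, they are 1.7 in controls. In the unseen-value rows, return at each visit depends on that visit's own value with slope 0.8. With 90% of 3-month responders returning at random, the 9-month SE falls by 0.1%. Monte Carlo error of a bias is about 0.078/√1000 = 0.0025.

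**At 3 months.** The SE does not change when nobody returns only the 9-month survey. It falls by 3.0% (correlation 0.6) or 9.0% (0.8) when return is independent at the two visits. Under the unseen-value mechanism the bias is about -0.18 SD for both methods.

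**Hand check of precision.** Given baseline, the 3-9 month correlation is r = (0.6 - 0.25)/(1 - 0.25) = 0.467, or (0.8 - 0.25)/0.75 = 0.733. If 80% of 3-month responders return, the variance ratio, joint to separate, is about 1 - r² × (1 - 0.8). That is 1 - 0.218 × 0.2 = 0.956 (SE -2.2%) and 1 - 0.538 × 0.2 = 0.892 (SE -5.5%), against simulated -2.1% and -4.8%.

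**Hand check of bias.** Bias should scale with r: 0.048 × 0.733/0.467 = 0.075, against simulated 0.078.

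**No true effect.** A second set of simulations used 600 trials per scenario, 37.5% missing at 3 months, further loss at 9 months, correlations of 0.5-0.7, and return depending on the 3-month value in one arm. Separate regression was biased by -0.029, -0.038 and -0.062 SD; the joint model by -0.005, +0.004 and -0.003. The variance ratio, separate to joint, was 1.01-1.07, so the joint SE was 0.5-3.3% lower (1 - 1/√1.01 to 1 - 1/√1.07).

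**The case against.** The strongest reply is that baseline-adjusted regression is a standard method, the SAP is not shown (20.5 says it will be agreed with the DMC), and the protocol never says that only complete cases will be used. It also plans sensitivity analyses for loss to follow-up. Part of this stands. Complete-case use is an inference from the default behaviour of the named method, and the protocol has not ignored drop-out. But the method itself is stated, and a sensitivity analysis under unnamed assumptions leaves the main estimate as it is.

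Three stronger readings are tempting, and the documents do not support them.

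- **That separate regression is valid only if 9-month return is unrelated to 3-month status.** It is also unbiased when return depends only on covariates in the model, or when there is no true effect and drop-out works the same way in both arms. With a true effect and the same mechanism in both arms, the bias was only +0.013 SD. Nothing in the protocol shows that the mechanism differs by arm.
- **That the joint model is generally less biased and more precise.** If people who relapse after month 3 stop replying because of that relapse, non-return depends on the unseen 9-month value and most of the bias remains (-0.146 to -0.168 against -0.160 to -0.204 SD).
- **That 35-40% non-response applies throughout.** It is the 3-month expectation only.

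It is also fair to say that the simulations assume normal data, whereas 17.2.4 itself allows for substantially skewed outcomes.

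**Conclusion.** The point holds as a low-cost improvement to secondary analyses, not as an error in the plan. For outcomes measured at both follow-ups, the joint model was never materially worse in any scenario tried. It cut the 9-month SE by about 0-9% and removed about 0.03-0.08 SD of 9-month bias when drop-out depended on the 3-month value differently by arm. Against the simulated SEs, the -0.048 and -0.078 SD biases are 0.048/0.0778 = 0.6 and 0.078/0.0775 = 1.0 of a standard error. All these sizes rest on assumed correlations, 9-month response and drop-out slopes.

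The gain stops there. People who return neither survey contribute nothing under either method. The accelerometer is worn at 3 months only, and the process measures, urge to smoke included, are "issued to all participants by CTU at the baseline and 3 months" only, so these outcomes gain nothing. A reader might infer that the mediation analysis is compromised, but 17.2.4 builds it on change from baseline to 3 months, while the bias shown here is at 9 months. The proportion halving their smoking is a binary outcome under logistic regression, which this linear model does not touch. The primary outcome and N=900 are unaffected.

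**What to change.** In 17.2.4, for daily cigarettes, 7-day activity recall, weight/BMI, EQ-5D-5L and SF-12, make the main analysis one repeated-measures linear model of the 3- and 9-month values. Include arm, time, arm-by-time, baseline value by time, site, HSI and the covariates already listed (age, gender, socio-economic status, level of smoking, recent quit attempts), with an unstructured covariance matrix. Report the arm difference with its 95% confidence interval at each visit. Everyone with at least one follow-up value then contributes.

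Keep the separate regressions and the planned loss-to-follow-up analyses as sensitivity analyses. Among the latter, include at least one that lets non-return depend on the unseen value, since the joint model does not cover that case. Outcomes with a single follow-up stay as planned.

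The cost is a wording change and a little more programming, with no new data. The price in assumptions is joint normality of the two follow-up values, so substantially skewed outcomes still need the separate handling that 17.2.4 anticipates.
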